We will use a mixed models approach to examine **secondary outcome measures (Specific Aim 2)** for a statistically significant difference in; drinks per week, and heavy drinking days per week, the outcomes used in the pilot study. The model will include fixed effects for medication group, week, and the interaction between medication and week, also controlling for pre-treatment drinking behavior data, and using a random effect for intercept. We will incorporate a grace period corresponding to the time it takes to titrate the medication to target dose into the models, and we will focus the primary analysis on the 8 weeks of treatment at the target dose. Aggregate outcome measures such as the percentage of heavy drinking days, which can be examined using several different methods, will be considered. A statistically significant difference on any of the secondary measures of both heavy drinking and drinking, with clinically significant effect sizes, will be considered a relative success for the medication. Additional secondary outcome measures will include changes in GGT level, measures of alcohol urge or craving to use (AUQ), measures of depression and anxiety, measures of physical health and quality of life (Q-LES-Q, the and the RAND-36) and level of alcohol-related problems (as measured on the SIP). These can also be performed with the mixed models approach. Statistical models evaluating time to relapse, drinking trajectories, percentage of abstinent days, drinks per drinking day, and total abstinence rates will be considered. **We will use the Bonferroni correction for the secondary outcomes and additional comparisons to guard against chance findings.**

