All secondary outcome analyses will be by intention to treat, a conservative approach that is aimed at avoiding an overestimation of the treatment effect and will include all subjects that take any medication and provide drinking data for at least one week. The use of multilevel repeated measure statistical models may increase the study power and potential to detect a treatment effect. This type of repeated-measures analysis 1) provides missing-data imputation procedures that are both conservative and logical; 2) allows for the measurement of the exact time that a given patient is measured at baseline and follow-up points, which need not be the same among patients; 3) plots and analyzes linear and non-linear time-course functions both overall and for subgroups of patients based on each patient's best estimate linear and non-linear regression line plots. We will use all available data on individuals and thus dropouts provide data until the point of dropout. The best-fitting variance-covariance structure between the repeated measures will be selected based on Schwartz-Bayesian Information Criterion (BIC). We will compare dropout patterns between groups and if there are concerns of informative dropout and/or informative intermittent missing data, we will use pattern mixture models (Hedeker and Gibbons, 1997) to perform sensitivity analyses to our main analyses. Adherence to the medication will be evaluated and factored into the analysis. We will evaluate and compare both medication conditions (placebo, ZNS) for percentage of prescribed pills taken. We do not expect a difference, but if one is found, we can then perform additional analysis on the main outcome variables to estimate treatment effects adjusted for percent pills taken. The number of MM sessions attended will be recorded and analyzed similar to the medication adherence.

The three-month follow up data will be gathered using a retrospective TLFB at the follow-up time point, and will be analyzed using logistic regression for PSNHDD, and either linear mixed models or Hierarchical Linear Modeling (HLM) for other outcomes. We will examine that drinking data between the end of treatment and the three-month time point and use the same outcomes as the main analysis. We will be able to examine for persistent effects of ZNS on drinking behavior and related outcomes. These analyses will include pre-treatment and within-treatment drinking data as covariates to evaluate the post-treatment effects of ZNS.

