6.I.6. Sample Size And Power Estimate (Specific Aims 1-3):

For the primary outcome PSNHDD: Based on the trend in the pilot study favoring ZNS with 12 subjects in the ZNS group without relapse to heavy drinking, and only 7 in the placebo group, we estimated the power with the previously planned sample size. Based on these proportions, we should be well powered (>89%) to detect a difference in PSNHDD with 80 in each group. Since dropouts will be counted as relapsed to heavy drinking, we will still be powered at that level, regardless of the number of dropouts. Even in the event that we don't recruit as many subjects as expected (e.g., N=64 in each group, approximately) we estimate the estimated power will be about 76% to detect a difference between the medication and placebo.

For secondary outcomes: Based on the effect sizes from our pilot study of ZNS (showing a small effect size on heavy drinking and a moderate effect size on total drinking), we estimated that a study with **N=160** (subjects) would be well powered (>.98) to detect a significant difference on the secondary outcomes heavy drinking days per week, and total drinks per week. In our pilot study we ran a linear mixed models and found a decrease in drinking of 1.4 drinks per week for the controls versus 2.2 drinks per week for ZNS. The variance in the decrease in drinking (slope) was approximately 0.9. Assuming similar results, a Monte Carlo simulation in Mplus showed that with a sample of 160 subjects evenly split between groups and measured weekly over 12 weeks there is power of 0.98 to detect a significant difference in slopes between groups. Also, in our pilot study we found a decrease in heavy drinking days per week of 0.2 for the controls versus 0.3 for ZNS. The variance in the decrease in drinking (slope) was about 0.1. Assuming similar results, a Monte Carlo simulation in Mplus showed that with a sample of 160 subjects evenly split between groups and measured weekly over 12 weeks there is power of 0.99 to detect a significant difference in slopes between groups. **Even if dropouts reached 40%, we will be well powered (>.80) for detecting differences on secondary outcomes.**

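### The secondary mixed model names a random intercept but no random slope, so a linear medication-by-week test would reject too often: about 7–12% at nominal 5% for drinks per week over 8 weeks

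*Combined protocol and SAP*

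**What the plan says.** Section 6.I.2 gives the model for drinks per week and heavy drinking days per week. It has "fixed effects for medication group, week, and the interaction between medication and week", adjusts for pre-treatment drinking, and is fitted "using a random effect for intercept". The main analysis is confined to 8 weeks at target dose. The section does not say whether week is linear or categorical, or which term decides success.

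Later in the same section, on covariance: "The best-fitting variance-covariance structure between the repeated measures will be selected based on Schwartz-Bayesian Information Criterion (BIC"). No candidate structures are listed. The section also says that such models can use "each patient's best estimate linear and non-linear regression line plots", but this describes the method in general and does not put a random slope in the model.

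Section 6.I.6 powers these two outcomes on differences in slope. For drinks per week the pilot "found a decrease in drinking of 1.4 drinks per week for the controls versus 2.2 drinks per week for ZNS", and "The variance in the decrease in drinking (slope) was approximately 0.9". For heavy drinking days it reports "a decrease in heavy drinking days per week of 0.2 for the controls versus 0.3 for ZNS", and "The variance in the decrease in drinking (slope) was about 0.1". Stated power is 0.98 and 0.99, with 160 patients and 12 weekly measurements.

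Section 6.I.2 applies Bonferroni to the secondary outcomes without giving the number of tests. It counts a significant drinking result with a clinically meaningful effect size as a partial success for the drug.

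**The concern.** The power calculation treats patients as differing in their rate of change, but the model as written does not. A random intercept with independent residuals takes patient-to-patient variation in slope for week-to-week noise. That noise averages out over all patient-weeks, whereas slope variation averages out only over patients. The standard error of a linear medication-by-week term is then too small and its p-value too low.

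At stake is a false claim of benefit on the outcomes that can earn the partial-success verdict. The stake rises if drinks per week is the primary measure, as Specific Aim 1 says. Section 6.I.2 names the percentage of subjects with no heavy drinking days (PSNHDD) instead.

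**Working it through.** **Inputs from section 6.I.6.** There are 80 patients per arm. Slope differences are 2.2 − 1.4 = 0.8 (drinks) and 0.3 − 0.2 = 0.1 (heavy drinking days). Slope variances τ² are 0.9 and 0.1, read as variances between patients.

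**Assumptions.** The within-patient residual variance σ² is not given, so a range is used. Tests are two-sided at 5%, data are complete, and week is linear.

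**1. The plan's power.** With T weekly measurements, Sxx = T(T² − 1)/12, which is 143 for T = 12 and 42 for T = 8. The slope difference has SE = √[2(τ² + σ²/Sxx)/80].
- Drinks, no residual error: SE = √(2 × 0.9/80) = 0.15, and 0.8/0.15 = 5.33, so power is 0.9996. This is an upper bound. Power of 0.98 needs σ²/143 = 0.689, so σ² = 98.5 and the residual SD is about 9.9. The stated 0.98 is attainable and implies that SD.
- Heavy drinking days, no residual error: SE = √(2 × 0.1/80) = 0.05, and 0.1/0.05 = 2, so power cannot exceed 0.52. The stated 0.99 does not reproduce. Reading 0.1 as an SD (τ² = 0.01) gives power above 0.999 without residual error, and 0.99 at a residual SD of about 1.3.

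**2. Type I error of the random-intercept slope test.** The true variance of a patient's fitted slope is τ² + σ²/Sxx. The random-intercept fit uses τ²/(T − 1) + σ²/Sxx. With R as their ratio, type I error = 2[1 − Φ(1.96/√R)].

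Example: drinks, T = 8, σ² = 98.5. Here σ²/Sxx = 98.5/42 = 2.346, so R = (0.9 + 2.346)/(0.129 + 2.346) = 1.31 and 1.96/√1.31 = 1.71, giving 8.7%.

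| Outcome (8 weeks) | τ² | σ² | R | Type I error |
|---|---|---|---|---|
| Drinks per week | 0.9 | 50 | 1.58 | 12.0% |
| Drinks per week | 0.9 | 98.5 | 1.31 | 8.7% |
| Drinks per week | 0.9 | 200 | 1.16 | 6.9% |
| Heavy drinking days, 0.1 a variance | 0.1 | 1 | 3.25 | 27.7% |
| Heavy drinking days, 0.1 a variance | 0.1 | 4 | 1.78 | 14.2% |
| Heavy drinking days, 0.1 an SD | 0.01 | 0.56 | 1.58 | 11.9% |
| Heavy drinking days, 0.1 an SD | 0.01 | 1 | 1.34 | 9.0% |
| Heavy drinking days, 0.1 an SD | 0.01 | 4 | 1.09 | 6.0% |

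The 6–12% range under the SD reading extends down to a residual SD of 0.75 (σ² = 0.56). At that same value the variance reading gives 33%.

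**3. BIC selection.** Null trials were simulated, 600 per setting (simulation error about 0.9 points at 5%), for drinks per week over 8 weeks. Candidates were random intercept, AR(1), random intercept plus AR(1), and unstructured, with or without a random-slope model.

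| Residual SD | BIC, no random-slope candidate | BIC, random slope a candidate | Random slope always fitted |
|---|---|---|---|
| 5 | 13.0% | 5.8% | 5.8% |
| 9.9 | 7.5% | 7.0% | 5.0% |
| 15 | 6.7% | 6.7% | 5.7% |

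At SD 9.9, with the random slope available, BIC still chose the plain random intercept in 319 of 600 trials. Across all ten settings simulated (both outcomes, 8 and 12 weeks), the random-slope model gave 3.7–5.8%. An unstructured covariance gave 4.8–8.3%, which is why it needs small-sample degrees of freedom.

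**4. Bonferroni.** For drinks per week over 8 weeks at SD 9.9 (√R = 1.145):
- Two tests, target 2.5%: 2.241/1.145 = 1.957, so the actual rate is 5.0%.
- Nine tests (a count of the measures named in 6.I.2, since the plan gives none), target 0.05/9 = 0.56%: 2.773/1.145 = 2.42, so the actual rate is 1.6%.

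**5. Average difference.** Testing the mean difference over the 8 weeks, with slope variance 0.9, gave a simulated 4.4%. Slope variation does not distort that test.

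**The case against.** The strongest reply is that the plan does not commit to the faulty model. BIC chooses the covariance structure, patient-level regression lines are mentioned, and nothing excludes a random slope. This stands in part: the defect is under-specification, and a random slope among the candidates brings the simulated rate for drinks per week to about 6–7% over 8 weeks. It is not a full answer, because the only random effect written down is the intercept, and BIC often keeps that model even when the slope is offered.

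The deciding test is also not named. If it is the average difference, or if week is categorical, the slope-test figures do not apply. The pilot's slope variance, and with it the inflation, may not carry over to the weeks at target dose.

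Bonferroni lowers the level, so the drinks-per-week rate at residual SD 9.9 need not exceed 5%. It does not repair the standard error: the rate is still about 2 to 3 times its corrected target.

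A reader might infer that the interaction test will be falsely significant far more than 5% of the time. The documents do not support that. Rates such as 17% for drinks (12 weeks, SD 9.9) belong to the power simulation's 12-week span, not the planned 8 weeks. The highest rates for heavy drinking days need a slope variance of 0.1, which the plan's own power of 0.99 contradicts.

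**Conclusion.** The point holds as a gap in the specification of secondary analyses. A random slope is neither named nor guaranteed, although the plan's power calculation relies on slope variation. If the linear medication-by-week term is the test, the stated model gives a type I error for drinks per week of about 7–12% at nominal 5% over 8 weeks. For heavy drinking days the size turns on whether 0.1 is a variance or an SD, and the stated power suggests an SD.

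Every rate is conditional on the assumed residual variance, complete data, linear week, and pilot slope variances that carry over.

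This should be fixed, but it is not critical while section 6.I.2 makes PSNHDD, analysed by logistic regression, the primary outcome. A reader might infer that the primary test is compromised. That would follow only if Specific Aim 1 governs, and the two sections must be reconciled.

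**What to change.** In section 6.I.2:
- Pre-specify a random intercept and a random slope for week. Alternatives are an unstructured covariance with small-sample degrees of freedom, or robust standard errors.
- List the BIC candidates and limit them to structures that include the random slope.
- State whether week is linear or categorical, and name the contrast that decides success. If it is the average difference over the 8 weeks, define it explicitly; with an interaction in the model, the medication coefficient equals that average only when week is centred.
- Give the number of tests that Bonferroni covers.

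In section 6.I.6, say whether 0.1 is a variance or an SD, and state the residual variance used in the simulations.

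The cost is a few sentences before unblinding and slightly larger p-values for the slope test. No new data are needed.

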We will use the percentage of subjects with no heavy drinking days (**PSNHDD**) as the primary outcome variable. This outcome is the FDA recommended endpoint for pivotal trials, and is described in Falk et al., (2010). The PSNHDD can be derived from each subject's TLFB data. An important initial consideration in considering effectiveness will be to identify baseline differences between groups that may have occurred despite randomization. **Successful outcomes during the treatment trial will be defined in terms of a statistically significant difference on the primary outcome measure: PSNHDD, compared during the 8 weeks of active treatment at the target dose, allowing for a 6 week grace period for the medication titration.** For all analyses, heavy drinking days will be defined as follows; for men > 5 drinks in a day and for women > 4 drinks in a day. Patients will be followed irrespective of whether they continue to receive medication treatment, so that analysis will include all data available for the 8-week treatment period. The analysis will be **intent-to-treat**, and dropouts will be considered as having relapsed to heavy drinking. We will use a logistic regression analysis with PSNHDD as a categorical dependent variable. Medication condition (placebo or ZNS) will be the main independent variable, and we will include the variables of early onset of alcoholism (EOA, binary), and the use of additional psychotropics (e.g., antidepressants, a binary variable) as covariates. The α will be set at .05 for the primary outcome variable. Between site differences will be explored.

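### A secondary drinking result can be declared a relative success for zonisamide even when the primary outcome fails, because the rule in section 6.I.2 is not gated on PSNHDD

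*Combined protocol and SAP*

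**What the plan says.** Section 6.I.2 sets the main criterion: "Successful outcomes during the treatment trial will be defined in terms of a statistically significant difference on the primary outcome measure: PSNHDD". On the error rate it says "The α will be set at .05 for the primary outcome variable". It does not say whether the test is one- or two-sided.

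The same section, under the secondary outcomes for Specific Aim 2, names two mixed-model outcomes: "drinks per week, and heavy drinking days per week, the outcomes used in the pilot study". It adds that aggregate measures such as the percentage of heavy drinking days may be looked at. The second criterion follows: "A statistically significant difference on any of the secondary measures of both heavy drinking and drinking". If the size of the effect also matters clinically, such a result "will be considered a relative success for the medication". No threshold for a clinically significant effect size is given, and the rule carries no condition on PSNHDD.

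After the non-drinking secondaries comes a further group: "Statistical models evaluating time to relapse, drinking trajectories, percentage of abstinent days, drinks per drinking day, and total abstinence rates will be considered". The paragraph closes with the multiplicity provision: "We will use the Bonferroni correction for the secondary outcomes and additional comparisons to guard against chance findings". The number of tests in the family is not stated.

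Section 3 assigns the roles differently. Specific Aim 1 there makes drinks per week the primary outcome, and Specific Aim 2 lists PSNHDD among the secondary ones.

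**The concern.** The plan has two ways to say that the drug worked, and the second stays open after the first has failed. The primary uses .05 and the secondary family, even when properly corrected, uses another .05. Bonferroni inside the secondary family cannot bring the chance of either claim back to .05.

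What is at stake is the conclusion the trial may draw. If PSNHDD is not significant, the text as written still permits a statement of success for zonisamide from a secondary drinking measure. The effect-size requirement could have prevented this, but its threshold can be chosen after the results are known. The unresolved choice of primary between sections 3 and 6.I.2 makes it easier still to pick the headline result afterwards.

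**Working it through.** **Inputs.**
- Primary α = .05 (6.I.2), taken as two-sided.
- Two named secondary drinking measures (6.I.2).
- Eight drinking measures in all: the two named, percentage of heavy drinking days counted once, and the five models that may be considered.
- Secondary level .05/d with Bonferroni divisor d. The plan does not state d.
- The correlation between test statistics is not in the documents. I assume one common value and show 0, 0.5 and 0.8.
- The effect-size condition is assumed never to bind, so every rate below is a ceiling.

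**The plan's own figure.** A single PSNHDD test at .05 has a false-positive rate of .05, which reproduces the stated level. The question is what the second route adds.

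**Secondary route alone, independent tests, divisor matched.** 1 − (1 − .05/k)^k. For k = 2: 1 − 0.975² = 0.049. For k = 8: 1 − 0.99375⁸ = 0.049. Bonferroni does its job within the family.

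**Either route, two-sided, independent tests.** 1 − 0.95 × (1 − .05/k)^k.
- k = 2: 1 − 0.95 × 0.9506 = 0.097.
- k = 8: 1 − 0.95 × 0.9511 = 0.097.
- Upper bound whatever the correlation: .05 + .05 = .10.

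**Either route, counting only false results that favour zonisamide.** 1 − 0.975 × (1 − .025/k)^k. For k = 2: 1 − 0.975 × 0.9752 = 0.049. The comparable figure for the primary alone is 0.025.

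**Allowing for correlation** (equicorrelated normal test statistics, no drug effect):

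| Measures tested | Divisor | Direction | ρ = 0 | ρ = 0.5 | ρ = 0.8 |
|---|---|---|---|---|---|
| 2 | 2 | either | 0.097 | 0.087 | 0.070 |
| 8 | 8 | either | 0.097 | 0.080 | 0.059 |
| 2 | 2 | favours zonisamide | 0.049 | 0.043 | 0.035 |
| 8 | 8 | favours zonisamide | 0.049 | 0.040 | 0.029 |
| 8 | 2 | either | 0.224 | 0.166 | 0.103 |

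The last row is a conditional worst case: all eight measures tested, but the divisor set to 2. At ρ = 0 it is 1 − 0.95 × 0.975⁸ = 0.224.

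**The other reading of the rule.** The word *both* may mean that one heavy-drinking measure and one overall-drinking measure must each be significant. With two measures at .025 and independence, the joint probability is 0.025² = 0.0006, and the two routes together give 1 − 0.95 × (1 − 0.0006) = 0.051. Across the correlations, with a matched divisor, the range is 0.051 to 0.053.

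**The case against.** A reader might infer that a false success for zonisamide is well above .05. The documents do not support that, for four reasons.

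- **Direction.** The two-sided figures of 0.06 to 0.10 include results favouring placebo, which nobody would call a success for the drug. In the favourable direction the rate stays at or just below .05 when the divisor is matched. The fair comparison there is with 0.025.
- **Safeguards in the same paragraph.** The rule also requires a clinically significant effect size, and Bonferroni is promised for the secondaries and additional comparisons. Both lower the rate. If the seven non-drinking secondaries (GGT, AUQ, depression, anxiety, Q-LES-Q, RAND-36, SIP) are counted with the eight drinking measures, the divisor is 15. The drinking route then spends at most 8/15 × .05 = .027.
- **The large figures.** Rates of 0.10 to 0.22 need eight measures tested with a divisor of 2. The plan never states that divisor, and its Bonferroni sentence points the other way. The relative-success sentence also comes before the five further models, so it is not clear that they feed the rule.
- **The label.** Relative success is weaker than the success reserved for PSNHDD. The .05 is stated for the primary only, so no stated trial-wide level is broken. A separate α for a corrected secondary family is common practice.

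All of this stands, and it limits the size of the problem. It does not supply the missing condition: nothing in 6.I.2 stops a success statement about the medication after PSNHDD has failed. A rule whose false-positive rate is about 0.05 on one reading and up to 0.10 on another also needs rewording.

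**Conclusion.** The concern holds as a defect in the success rule. Section 6.I.2 allows a relative success to be declared on secondary drinking measures whatever PSNHDD shows. With Bonferroni at a matched divisor, the two-sided chance of either false claim is about 0.06 to 0.10, or 0.03 to 0.05 against 0.025 in the direction favouring zonisamide. It is about 0.05 if one measure of each kind is required. It would reach 0.10 to 0.22 only if all eight measures were tested with a divisor of 2.

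These figures rest on a two-sided .05, equal correlations between 0 and 0.8, and an effect-size condition that never binds. The open list and unstated divisor mean that the matched-divisor assumption cannot be verified from the plan, but they do not show that it will be broken. The missing gate is the main point. It should be corrected before the data are unblinded.

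**What to change.** 1. Reconcile section 3 (drinks per week primary, PSNHDD secondary) with section 6.I.2 (the reverse) and declare one primary outcome.
2. Delete the relative-success sentence. Test the declared primary at two-sided .05.
3. Only if it is significant, test the two powered secondaries confirmatorily with a Bonferroni divisor of 2, that is, at .025 each. If PSNHDD is the primary, these are drinks per week and heavy drinking days per week, for which section 6.I.6 gives power. If drinks per week becomes the primary, the pair must be redefined.
4. Label every other measure listed or considered in 6.I.2 as exploratory, and report it with estimates and confidence intervals.
5. If the primary is not significant, report secondary results as supportive or hypothesis-generating, not as a success of the medication.

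The cost is SAP wording, with no change to data collection, sample size or conduct. The real loss is that relative success can no longer be claimed after a failed primary. There is a partial gain when the primary succeeds. If the current family is the two named drinking measures plus the seven non-drinking secondaries, each key secondary is now tested at .05/9 = .0056, and this rises to .025.

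### The Bonferroni family for the secondary outcomes is never closed, so the threshold behind the relative-success claim is not fixed, and the secondary power is stated without an alpha

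*Combined protocol and SAP*

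**What the plan says.** Section 6.I.2 sets the primary test level: "The α will be set at .05 for the primary outcome variable". For the secondary outcomes it says "We will use the Bonferroni correction for the secondary outcomes and additional comparisons". It gives no number of comparisons and no adjusted alpha.

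The outcomes that could fall under the correction, all in 6.I.2, are:
- two main drinking outcomes: "drinks per week, and heavy drinking days per week, the outcomes used in the pilot study";
- seven further named measures: GGT, AUQ craving, depression, anxiety, Q-LES-Q, RAND-36 and SIP;
- about six that are only to be considered: percentage of heavy drinking days (method left open), time to relapse, drinking trajectories, percentage of abstinent days, drinks per drinking day, and total abstinence;
- unspecified additional comparisons.

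The same section attaches a claim to these tests. "A statistically significant difference on any of the secondary measures of both heavy drinking and drinking", provided the effect sizes are clinically significant, "will be considered a relative success for the medication". No effect-size cut-off is given.

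Section 6.I.6 reports simulations for the two main drinking outcomes with 160 subjects measured weekly over 12 weeks. For drinks per week, "there is power of 0.98 to detect a significant difference in slopes between groups"; for heavy drinking days per week the figure is 0.99. With dropout of up to 40%, "we will be well powered (>.80) for detecting differences on secondary outcomes". No alpha, sidedness, residual variance or multiplicity adjustment is stated for any of these figures.

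**The concern.** Bonferroni divides alpha by the number of tests. Until that number is fixed, no threshold exists, and the choice can be made after the results are known. Because a success label depends on significance at that threshold, the same data could earn the label or miss it according to how many outcomes are counted.

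The second issue is whether the stated secondary power applies to the tests that will be run. The simulations are reported as if each outcome stood alone. If they used an unadjusted 0.05, the power is lower than stated, and the drop grows with every outcome added to the family. The two drinking outcomes, the only secondaries with a power calculation, would then lose power to quality-of-life and laboratory measures that have none.

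**Working it through.** **Inputs.** From 6.I.6: 80 per arm; slope difference in drinks per week 2.2 − 1.4 = 0.8, slope variance 0.9; slope difference in heavy drinking days per week 0.3 − 0.2 = 0.1, slope variance 0.1; stated powers 0.98, 0.99 and above 0.80 at 40% dropout. Assumed, because not stated: two-sided 0.05 behind those powers.

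**Step 1: can the stated powers be reproduced?** The residual variance is not given, so only an upper bound is available, with residual variance set to zero: power ≤ Φ(difference / √(2 × variance / 80) − 1.960).
- Drinks per week: √(2 × 0.9 / 80) = 0.15; 0.8 / 0.15 = 5.333; Φ(5.333 − 1.960) = 0.9996. So 0.98 is attainable. It corresponds to a total slope variance of 40 × (0.8 / 4.014)² = 1.589. With 12 weekly measures (sum of squares of time 143), the residual variance is (1.589 − 0.9) × 143 ≈ 98.5, an SD of about 9.9 drinks per week. The documents neither confirm nor exclude that. Even at alpha 0.05/20 the upper bound is Φ(5.333 − 3.023) = 0.990, so 0.98 does not reveal which alpha was used.
- Heavy drinking days per week: √(2 × 0.1 / 80) = 0.05; 0.1 / 0.05 = 2.0; Φ(2.0 − 1.960) = 0.516 (0.639 one-sided). So 0.99 cannot come from the stated inputs, even without correction. It becomes attainable only if 0.1 is an SD rather than a variance.

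**Step 2: effect of the correction, taking the stated powers at face value.** Implied noncentrality = 1.960 + z(power): 1.960 + 2.054 = 4.014 for 0.98, and 1.960 + 2.326 = 4.286 for 0.99. Power with m tests = Φ(noncentrality − c), where c = z(1 − 0.05/(2m)).

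**Step 3: 40% dropout.** Noncentrality is multiplied by √0.6 = 0.775, giving 3.109 and 3.320. This removes 40% of subjects entirely.

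In the power columns, the first figure is drinks per week and the second is heavy drinking days per week.

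| m | Per-test alpha | c | Power, full N | Power, 40% lost |
|---|---|---|---|---|
| 1 | 0.05 | 1.960 | 0.980 / 0.990 | 0.875 / 0.913 |
| 2 | 0.025 | 2.241 | 0.962 / 0.980 | 0.807 / 0.860 |
| 3 | 0.0167 | 2.394 | 0.947 / 0.971 | 0.763 / 0.823 |
| 4 | 0.0125 | 2.498 | 0.935 / 0.963 | 0.730 / 0.795 |
| 9 | 0.0056 | 2.773 | 0.893 / 0.935 | 0.632 / 0.708 |
| 15 | 0.0033 | 2.935 | 0.860 / 0.912 | 0.569 / 0.650 |

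The second figure in each pair inherits the 0.99 that Step 1 could not reproduce. It shows only what the correction would do to that claim.

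**The case against.** Four points can be made for the plan.

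First, a reader might infer that the secondary power was computed without any correction. The documents do not say so. Section 6.I.6 is silent on alpha, and Step 1 shows that 0.98 is attainable even at 0.05/20. This stands: what is established is that the alpha is unstated, and the losses in the table are conditional on 0.05.

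Second, a reader might take the above-0.80 statement at 40% dropout as exactly 0.80 and then correct it, which gives about 0.71, 0.51 and 0.45 with 2, 9 and 15 tests. The plan gives 0.80 as a floor, so those figures overstate the loss. Scaling from 0.98 and 0.99 is fairer. Even that is pessimistic, because 6.I.2 keeps each dropout's data up to the point of dropout.

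Third, a reader might infer that significance on any single drinking measure is enough for the success label. The sentence also refers to both heavy drinking and drinking and requires clinically significant effect sizes. It may mean one measure in each domain, which is stricter. The wording is ambiguous, and the threshold is open under either reading. Nor does the label decide the trial: 6.I.2 defines a successful outcome by the primary measure, the percentage of subjects with no heavy drinking days (PSNHDD).

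Fourth, Bonferroni is valid and conservative, and correcting over a broad family is a legitimate choice. That is so, and choosing it is not an error. The defect is that the family is not closed. Holm is recommended because it gives the same familywise control and never rejects less. At full N the stated power also stays above 0.80 up to 15 tests, so the correction alone does not leave the secondary analyses underpowered.

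**Conclusion.** The concern holds for the threshold and, conditionally, for the power. The Bonferroni family is open, so the per-test alpha behind the relative-success label can lie anywhere from 0.025 to 0.0033 or below. That needs no assumption.

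Assuming the stated powers are at two-sided 0.05, the correction costs 1 to 2 percentage points with two tests, about 5 to 9 with nine, and about 8 to 12 with fifteen. The statement that fails is the one about dropout: with 40% of subjects lost, power falls below 0.80 for drinks per week from three tests and for both outcomes from four. With two tests it survives (0.807 / 0.860). Those figures also assume noncentrality proportional to the square root of N.

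The 0.99 for heavy drinking days is a separate and larger problem, since its stated inputs allow at most 0.516 before any correction. PSNHDD as defined primary in 6.I.2 is untouched by all this, so the point should be corrected but does not threaten the primary analysis.

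**What to change.** 1. Reconcile Specific Aim 1 in section 3, which makes drinks per week the primary outcome (with PSNHDD listed under the secondary Aim 2), with 6.I.2, which makes PSNHDD primary. The secondary family cannot be settled before that.
2. With PSNHDD confirmed as primary, name drinks per week and heavy drinking days per week as the only confirmatory secondary family and test it by Holm at two-sided 0.05: the smaller p-value against 0.025 and, if that is significant, the larger against 0.05. If a larger family is preferred, list it in full and state the number of tests.
3. Say whether relative success needs one or both of these outcomes, and give the effect-size cut-off.
4. Report the remaining secondaries as descriptive, with estimates and confidence intervals.
5. Restate the secondary power at the adjusted level, giving alpha, sidedness and residual variance, and simulate dropout as it will be analysed. Recompute the heavy-drinking-days figure from its inputs; do not rescale 0.99.

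The cost is revised analysis-plan wording and a rerun of the simulations, with no extra patients or data. The other secondaries lose any confirmatory claim, and the stated power becomes less favourable, possibly much less so for heavy drinking days.
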